7.5. Guidelines for Adjusting, Withholding, or Discontinuing Study Treatment

ASTX029 dosing should be withheld in the case of a DLT in Cycle 1 or toxicity in subsequent cycles that would have qualified as a DLT if it had occurred in Cycle 1. Dosing may resume, at the investigator's discretion, if and when study-treatment-related toxicity has:

- Completely resolved or
- Returned to baseline or partially recovered to ≤Grade 2 (anemia, fatigue, malaise, and alopecia) or returned to baseline or partially recovered to ≤Grade 1 (all other toxicities).

If and when a decision is made to resume dosing, the individual's dose should be adjusted to the previously assessed lower dose level that was considered safe by the DSRC. A maximum of 2 dose reductions are permitted for any single subject. In the event of further unacceptable toxicity, the investigator should consider discontinuation of study treatment for that subject.

If toxicity has not resolved as described above within 21 days, the investigator should permanently discontinue study treatment unless the subject is receiving compelling benefit, the

benefit of the study treatment exceeds the risks, and no alternative therapy is available. Approval by the Sponsor's medical monitor is required to restart study treatment after an interruption \geq 21 days, and study treatment must be administered at a dose approved by the Sponsor's medical monitor when toxicity has resolved as described above.

Suggested guidelines and criteria for adjusting, withholding, or discontinuing study treatment as a result of skin toxicities, ocular toxicities, diarrhea, liver toxicities, and LVEF decrease are provided in Appendix 4, Appendix 5, Appendix 6, Appendix 7, and Appendix 8, respectively. The institutional standards for the management of these toxicities can differ from the suggested guidelines. In this case, best clinical judgment should be applied.

7.6. Concomitant Treatment

On the concomitant medication eCRF, document all medications a subject takes starting from 14 days before study treatment initiation and ending 30 days after the last dose of study treatment. Include supportive or palliative treatment (see below) whether prescription or nonprescription, and medications taken for procedures (eg, biopsy). Include start and stop dates and indication.

7.6.1. Supportive, Prophylactic, or Other Treatments

All subjects receiving treatment with ASTX029 should continue to receive appropriate supportive care for the treatment of their cancer, according to the institutional standard practice or other established standard of care guidelines. Antiemetics and loperamide may be given to alleviate ASTX029-related toxicity on an as-required basis, and GI toxicity should not be considered to be dose limiting in the absence of maximal supportive therapy. Subjects receiving treatment with a bisphosphonate are not excluded from participating in the trial; bisphosphonate therapy may be initiated while maintaining treatment with ASTX029 provided the subject does not have disease progression according to RECIST v1.1 criteria. The subject may receive palliative radiotherapy to a symptomatic lesion during the study. All efforts should be made to reduce the radiation field to the smallest possible area of exposure. ASTX029 treatment should be interrupted during radiotherapy and resumed upon completion.

Any supportive treatment should be documented in the provided eCRFs.

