5.3. Exclusion Criteria

Subjects meeting any of the following criteria will be excluded from the study:

1. Hypersensitivity to ASTX029 or excipients of the drug product.

- 2. Poor medical risk in the investigator's opinion because of systemic diseases in addition to the cancer under study, for example, uncontrolled infections.
- 3. Life-threatening illness, significant organ system dysfunction, or other condition that, in the investigator's opinion, could compromise subject safety or the integrity of study outcomes or interfere with the absorption or metabolism of ASTX029.
- 4. Prior anticancer treatments or therapies within the indicated time window prior to first dose of study treatment (ASTX029), as follows:
 - a. Cytotoxic chemotherapy or radiotherapy within 3 weeks prior. Palliative radiotherapy to a single lesion within 2 weeks prior. Any encountered treatment-related toxicities (excepting alopecia) not stabilized or resolved to ≤Grade 1.
 - b. Monoclonal antibodies or biologics within 4 weeks prior. Any encountered treatmentrelated toxicities not stabilized or resolved to ≤Grade 1.
 - c. Molecularly targeted drug or other investigational drugs, without the potential for delayed toxicity, within 4 weeks of the first dose of study treatment or 5 half-lives (minimum 14 days), whichever is shorter. Any encountered treatment-related toxicities (excepting alopecia) not stabilized or resolved to ≤Grade 1.
- 5. Prior treatment with ERK inhibitors.
- 6. History of, or at risk for, cardiac disease, as evidenced by 1 or more of the following conditions:
 - a. Abnormal left ventricular ejection fraction (LVEF; <50%) on echocardiogram (ECHO) or multiple-gated acquisition (MUGA) scan.
 - b. Congestive cardiac failure of ≥Grade 3 severity according to New York Heart Association (NYHA) functional classification defined as patients with marked limitation of activity and who are comfortable only at rest.
 - c. Unstable cardiac disease including unstable angina or hypertension as defined by the need for overnight hospital admission within the last 3 months (90 days).
 - d. History or evidence of long QT interval corrected for heart rate (QTc), ventricular arrhythmias including ventricular bigeminy, complete left bundle branch block, clinically significant bradyarrhythmias such as sick sinus syndrome, second- and third-degree atrioventricular (AV) block, presence of cardiac pacemaker or defibrillator, or other significant arrhythmias.

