- Lesions that meet the criteria for radiographically defined simple cysts should not be considered as malignant lesions (neither measurable nor nonmeasurable) since they are, by definition, simple cysts.
- 'Cystic lesions' thought to represent cystic metastases can be considered as measurable lesions, if they meet the definition of measurability described above. However, if noncystic lesions are present in the same subject, these are preferred for selection as target lesions.

Lesions With Prior Local Treatment

Tumor lesions situated in a previously irradiated area, or in an area subjected to other loco-regional therapy, are not considered measurable unless there has been demonstrated progression in the lesion.

Specifications by Methods of Measurements

Measurement of Lesions

All measurements should be recorded in metric notation, using calipers if clinically assessed. All baseline evaluations should be performed as close as possible to the treatment start and NEVER more than 21 days before the beginning of the treatment.

Method of Assessment

The same method of assessment and the same technique should be used to characterize each identified and reported lesion at baseline and during follow-up. Imaging-based evaluation should always be done rather than clinical examination unless the lesion(s) being followed cannot be imaged but are assessable by clinical exam.

CT, MRI: CT is the best currently available and reproducible method to measure lesions selected for response assessment. This guideline has defined measurability of lesions on CT scan based on the assumption that CT slice thickness is 5 mm or less. When CT scans have slice thickness greater than 5 mm, the minimum size for a measurable lesion should be twice the slice thickness. Magnetic resonance imaging (MRI) is also acceptable in certain situations (eg, for body scans).

Tumor Response Evaluation

Assessment of Overall Tumor Burden and Measurable Disease

To assess objective response or future progression, it is necessary to estimate the overall tumor burden at baseline and use this as a comparator for subsequent measurements. In this study, only subjects with measurable disease at baseline should be included in the study.

Baseline Documentation of 'Target' and 'Nontarget' Lesions

When more than 1 measurable lesion is present at baseline, all lesions up to a maximum of 5 lesions total representative of all involved organs should be identified as target lesions and will

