If a new lesion is equivocal, for example because of its small size, continued therapy and follow-up evaluation will clarify if it represents truly new disease. If repeat scans confirm there is definitely a new lesion, then progression should be declared using the date of the initial scan.

Evaluation of Best Overall Response

The best overall response is the best response recorded from the start of the study treatment until the end of treatment. No confirmatory measurement for CR, PR, or SD is required in the study.

The subject's best overall response assignment will depend on the findings of both target and nontarget disease and will also take into consideration the appearance of new lesions.

Time Point Response

Please follow the per-protocol time point response assessments. Table 14 below provides a summary of the overall response status calculation at each time point for subjects who have measurable disease at baseline.

Time Point Response: Subjects with Target (±Nontarget) Disease			
Target Lesions	Nontarget Lesions	New Lesions	Overall Response
CR	CR	No	CR
CR	Non-CR/Non-PD	No	PR
CR	Not evaluated	No	PR
PR	Non-PD or not all evaluated	No	PR
SD	Non-PD or not all evaluated	No	SD
Not all evaluated	Non-PD	No	NE
Pd	Any	Yes or No	PD
Any	PD	Yes or No	PD
Any	Any	Yes	PD

Table 14:Overall Response

CR=complete response, NE=inevaluable, PD=progressive disease, PR=partial response; SD=stable disease.

Missing Assessments and Inevaluable Designation

When no imaging/measurement is done at a particular time point, the subject is not evaluable at that time point. If only a subset of lesion measurements are made at an assessment, usually the case is also considered not evaluable at that time point, unless a convincing argument can be made that the contribution of the individual missing lesion(s) would not change the assigned time point response. This would be most likely to happen in the case of PD. For example, if a subject had a baseline sum of 50 mm with 3 measured lesions and at follow-up only 2 lesions were assessed, but those gave a sum of 80 mm, the subject will have achieved PD status, regardless of the contribution of the missing lesion.

Best Overall Response: All Time Points

The best overall response is determined once all the data for the subject is known.

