In this study, tumor measurement will be conducted at the end of every 2 cycles (\pm 7 days) for the first 4 cycles and then every 4 cycles (\pm 1 cycle) thereafter until clinical and/or radiographic disease progression, or death, or the subject withdraws consent. Scan dates should not be adjusted or rescheduled due to dose interruption of any type.

Baseline tumor assessments must be performed within 3 weeks (21 days) prior to the first dose of treatment.

All efforts should be made to ensure consistency between the baseline measurements and all subsequent measurements in reference to utilization of scanning method, equipment, technique (including slice thickness and field of view), and radiographic interpreter.

The radiographic evaluation must include CT or MRI scanning of the known sites of involvement, as well as the chest, abdomen, and pelvis if they are not the primary target. Any additional suspected sites of disease should also be imaged. All evaluations should meet the standard of care for imaging of lesions in the respective organ(s) and should conform to the image acquisition guidelines according to institutional standards.

All target and nontarget sites are evaluated at each time point of tumor assessment.

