## 7.5.1 Overall Response and Disease Control Rate

The ORR will be calculated as the number of evaluable subjects whose best response is CR or PR, divided by the total number of subjects evaluable for ORR analysis (Section 5.3). The DCR will be calculated as the number of subjects whose best response is CR, PR, or SD, divided by the total number of subjects evaluable for DCR analysis (Section 5.3). The 90% Clopper-Pearson CIs for the ORR and DCR will be provided.

Best response for a subject is defined as the best overall response from all post baseline assessments of a subject in the study. When SD is believed to be the best response, it must also meet the protocol-specified minimum time from baseline (6 weeks). If the minimum time is not met when SD is otherwise the best time point response, the subject's best response depends on the subsequent assessments.

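### A target lesion irradiated after the baseline scan has no scoring rule, so radiation shrinkage can count as an unconfirmed response in the Phase 2 primary endpoint

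*Protocol*

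**What the plan says.** **Radiotherapy on study.** Protocol Section 7.6.1: "The subject may receive palliative radiotherapy to a symptomatic lesion during the study". It continues: "ASTX029 treatment should be interrupted during radiotherapy and resumed upon completion". The subject therefore stays on treatment and in response follow-up. Nothing limits the permission to non-target lesions. Section 7.6.2 bars other anticancer treatment except what the protocol itself provides for, and this radiotherapy is provided for.

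**Radiotherapy before dosing.** Exclusion criterion 4a in Section 5.3 rules out "Palliative radiotherapy to a single lesion within 2 weeks prior", so single-lesion palliative treatment before that window is allowed. For the scan, Appendix 3 says: "Baseline tumor assessments must be performed within 3 weeks (21 days) prior to the first dose of treatment".

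**The existing rule on irradiated lesions.** Under baseline measurability, Appendix 3 says: "Tumor lesions situated in a previously irradiated area, or in an area subjected to other loco-regional therapy, are not considered measurable". The exception is a lesion that has shown progression.

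**Response scoring.** Appendix 3 defines PR as a fall of at least 30% in the target sum from baseline, and adds: "No confirmatory measurement for CR, PR, or SD is required in the study". SAP 7.5.1 says: "Best response for a subject is defined as the best overall response from all post baseline assessments of a subject in the study". Appendix 3 runs best response from start to end of treatment. Neither window is cut at radiotherapy.

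**Use of the result.** Each Phase 2 cohort follows Simon's optimal design (Protocol Section 11.1, SAP Section 4.0): 10 subjects, 19 more if at least 2 respond, and rejection of an ORR of 10% or less if at least 6 of 29 respond.

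**The concern.** Appendix 3 gives rules for nodes, lesions too small to measure, lesions that split or merge, and missing lesions. It has none for a target lesion irradiated after it was measured at baseline. Protocol Section 11.6 and SAP Section 7.5 contain no not-evaluable rule, no cut-off of best response and no censoring for this case. An investigator who applies the text as written keeps measuring the lesion and keeps its diameter in the sum.

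The error runs mainly towards extra responders. With no control arm, a response produced by permitted local treatment cannot be told apart from drug effect. Stage 1 turns on 2 responses in 10, so a single case carries weight. The same lesion can also delay recorded progression and so lengthen PFS and duration of SD.

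A narrow version of the gap exists before dosing. A lesion can be measured on Day -21 and irradiated in the following week, before the 2-week exclusion begins. It was not previously irradiated when it was measured, so the baseline rule does not clearly catch it.

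**Working it through.** **Inputs.** From Protocol Section 11.1: n1 = 10, continue at 2 or more, n2 = 19, reject at 6 or more of 29, p0 = 0.10, p1 = 0.30, one-sided alpha 0.05, power 80%. From Appendix 3: PR at a 30% fall in the sum, and a maximum of five target lesions. Assumption, not in the documents: a fraction f of true non-responders independently gains a false PR.

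**1. Reproduce the design.** With X1 ~ Bin(10, p) and X2 ~ Bin(19, p):
- P(stage 2) = P(X1 ≥ 2). At p = 0.10 this is 1 − 0.9^10 − 10 × 0.1 × 0.9^9 = 0.264.
- P(reject) = Σ over x = 2 to 10 of P(X1 = x) × P(X2 ≥ 6 − x). This is 0.0471 at p = 0.10 and 0.805 at p = 0.30.

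Both agree with the stated 0.05 ceiling and 80% power.

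**2. Sensitivity to false PRs.** Apparent ORR at a true ORR of 10% is 0.10 + 0.90f.

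| f | apparent ORR | P(stage 2) | P(reject) |
|---|---|---|---|
| 0 | 0.100 | 26.4% | 4.7% |
| 1% | 0.109 | 29.9% | 6.6% |
| 2% | 0.118 | 33.4% | 8.9% |
| 3% | 0.127 | 36.9% | 11.6% |
| 5% | 0.145 | 43.7% | 18.1% |

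**3. Effect of one case, given that it occurs.** Fix one stage 1 subject as a false responder and leave the others at 10%:
- P(stage 2) = 1 − 0.9^9 = 0.613, up from 0.264.
- P(reject) = 0.128, up from 0.047.

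If the one false responder falls in stage 2 instead, P(reject) = 0.094.

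**4. When one lesion can produce a PR.** If the irradiated lesion is a share s of the baseline sum, shrinks by a fraction d, and the other lesions are unchanged, the sum falls by s × d. PR needs s × d ≥ 0.30.
- Illustration: lesions of 40 and 30 mm, with the 40 mm lesion falling to 18 mm. Here s = 40/70 = 0.571 and d = 22/40 = 0.55, so s × d = 0.314. The sum goes from 70 to 48 mm, a fall of 31.4%, which scores as PR.
- Two equal lesions: d ≥ 0.30/0.50 = 60%.
- Three equal lesions: d ≥ 0.30/(1/3) = 90%.
- Four or five equal lesions: s = 0.25 or 0.20, so PR is out of reach even if the lesion vanishes.

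**5. Pre-dose window.** The baseline scan may be 21 days before dosing, and single-lesion radiotherapy is barred for the last 14. The exposed interval is 21 − 14 = 7 days.

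**The case against.** A reader might infer that the plan has no rule at all for irradiated lesions. It does: Appendix 3 excludes those irradiated before baseline unless progression is shown. The pre-dose gap is therefore limited to scanning first and irradiating second within one week, and Appendix 3 works against that by asking for baseline evaluations as near to treatment start as possible.

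A reader might also note that starting a bisphosphonate is conditional on no RECIST progression while radiotherapy is not, and infer that a progressing lesion can be irradiated and the subject kept on drug. Section 5.4.1 says subjects who progress should not stay on study treatment, and response assessment ends at progression. The exposed group is non-progressing subjects with a symptomatic target lesion.

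The route to a false PR is also limited. The irradiated lesion must be a large share of the sum, there must be no new lesion and no non-target progression, and bone lesions without a measurable soft-tissue component cannot be targets. The DSRC reviews Phase 2 activity, the stated aim is preliminary activity, and Protocol Section 11 leaves room for sensitivity analyses.

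All of this bears on how often the problem arises, and it stands. None of it is a scoring rule: when the case does occur, the written text still counts it as a response. The lesion-share limit also assumes the other lesions do not change. If they shrink somewhat without reaching 30%, a smaller irradiated lesion could tip the sum.

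**Conclusion.** The gap is real for target lesions irradiated after the baseline scan, including the one-week case before dosing. It goes beyond missing detail, because applying the rules as written can give the wrong value for the primary endpoint.

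Its size is not known. The percentages for f between 1% and 5% are a sensitivity range on an assumed rate applied independently to non-responders. The documents do not support reading 11.6%, or any other entry, as the trial's actual false-positive rate. The rise from 26.4% to 61.3% for opening stage 2 is conditional on a false responder having occurred in stage 1; the probability of that event cannot be estimated from the documents. The 40 and 30 mm example shows that a false PR is possible, not that it is common. With the gap closed (f = 0), the design keeps its exact alpha of 4.7%.

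**What to change.** 1. **Appendix 3 and SAP 7.5.1.** Once a target lesion is irradiated after the baseline scan, later time points cannot be scored CR or PR. Best response rests on assessments before the radiotherapy, and the subject stays in the ORR denominator.
2. **Appendix 3.** A lesion irradiated between the baseline scan and C1D1 may not be a target lesion.
3. **SAP 7.5.2 and 7.5.3.** State how DOR, duration of SD and PFS treat these subjects, for example with a sensitivity analysis censoring at the last assessment before radiotherapy. Without this, a subject already in PR when irradiated has no clear DOR.
4. **eCRF.** Section 7.6.1 already requires supportive treatment to be recorded. Add one field for whether the irradiated site is a target lesion.

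The cost is a few sentences in each document and one data field. ORR may be slightly lower, and a true later response in unirradiated lesions would not count, so power would fall a little below 80.5% if any true responder is irradiated before first responding. When radiotherapy may be given, the scan schedule and the sample size all stay as they are.

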7.6.2. Prohibited Medications and Substances

Other anticancer treatments, including other investigational drugs or therapies, unless specified in the protocol, are prohibited.

ASTX029 is a substrate and inhibitor of cytochrome P450, family 3, subfamily A (CYP3A). Therefore, concomitant administration of drugs known to be strong CYP3A4 inhibitors or inducers has the potential to result in drug-drug interactions (DDIs) with ASTX029. Careful consideration should be given to balancing the medical needs of the subject and the potential effect on ASTX029 before coadministering a drug that is known to be a strong CYP3A4 inhibitors and inducers at ASTX029 dose levels that display clinical effects (toxicity or activity). Particular caution should be exercised when coadministering drugs with ASTX029 that are sensitive

CYP3A substrates with narrow therapeutic windows until the potential liability of ASTX029 for DDIs is fully qualified.

ASTX029 is an inhibitor of the liver uptake transporter OATP1B1. Therefore, concomitant administration of drugs known to be OATP1B1 substrates has the potential to result in DDIs with ASTX029. Particular caution should be exercised when coadministering drugs with ASTX029 that are sensitive OATP1B1 substrates with narrow therapeutic windows until the potential for DDIs via inhibition of OATP1B1 is fully understood.

Examples of CYP3A4 inhibitors and inducers and OATP1B1 substrates and inhibitors may be found on the following websites; note that the published lists are not comprehensive. Refer to the specific product information for an intended concomitant drug.

- FDA.gov: http://www.fda.gov/Drugs/DevelopmentApprovalProcess/DevelopmentResources/Dr ugInteractionsLabeling/ucm093664.htm (FDA 2020).
- Pharmacytimes.com: http://www.pharmacytimes.com/publications/issue/2015/december2015/druginteractions-with-cyp3a4-an-update (Horn and Hansen 2015).

Medications known to increase the risk of torsades de pointes should be used with caution. A list of such medications is provided at the following website and discussed in Drew et al (2010), https://www.crediblemeds.org/ (Woosley et al 2022). Any AV-nodal blocking medications (ie, beta-blockers, non-dihydropyridine calcium-channel blockers, and digitalis) should be used with caution. A list of such medications is provided and discussed in Wooten 2002 and by Vogler et al (Vogler et al 2012).

The VFR of ASTX029 contains ethanol and propylene glycol (Section 7.1.1). It is advisable to review concomitant medications that may interact with VFR ingredients.

Any medication considered necessary for the subject's safety and well-being may be given at the discretion of the investigator(s). However, if a subject requires treatment with a drug known to prolong the QT interval while on study and there is no alternative medication, the subject should be carefully monitored for potential QT prolongation for at least 24 hours. Investigators should also be aware that the list of medications that prolong the QT interval provided in the cited references is not exhaustive and there are other medications with a possible or conditional risk of causing QT prolongation and/or torsades de pointes.

Investigators should consult with the Sponsor's medical monitor regarding the potential concomitant use of QTc-prolonging agents with a known risk of torsades de pointes while on study treatment in individual subjects on a case-by-case basis.

Concomitant St. John's Wort, grapefruit, and grapefruit juice are also prohibited during treatment with ASTX029.

